Home-based tDCS for behavioral symptoms in Alzheimer's disease and related dementias

NCT05478681

Version Date: 08/27/2024

Protocol Title: Home-based tDCS for behavioral symptoms in Alzheimer's disease and related dementias

Principal Investigator: [name], PhD, UTHealth

Co-Investigators:

[name] [name], UT Health San Antonio

[name] [name], UT Health San Antonio

[name], UTHealth

[name], UTHealth

General Information

Study Title	Home-based tDCS for behavioral symptoms in Alzheimer's disease and related dementias (ADRD)	
Short Title	tDCS for behavioral symptoms in ADRD	
Study Design	
This is an open-label, non-randomized clinical trial to assess acceptability, safety and efficacy of providing transcranial direct current stimulation (tDCS) to Alzheimer's disease and related dementia (ADRD) patients with behavioral symptoms.
 
All participants will receive active tDCS with a constant current intensity of 2mA for 30 minutes, five times per week, for six weeks. Anodal tDCS will be applied to the left dorsolateral prefrontal cortex, while cathodal electrode will be positioned on the right dorsolateral prefrontal cortex. Caregivers will set up and administer tDCS for participants with AD at home. All sessions will be remotely supervised by trained research staff through video conferencing software. Participants will be assessed at baseline, treatment day 12, treatment day 28, treatment day 42, and 6 weeks
	

	post-treatment.	
Study Participants	Patients with ADRD and behavioral symptoms will be recruited at the UTHealth Neurosciences Neurocognitive Disorders Center ([name]), and UT Physicians Center for Healthy Aging ([name]).	
Planned Sample Size	20	
Planned Study Period	12 weeks	
	Objectives	Outcome Measures
Primary Goal	To assess acceptability, and safety of providing tDCS to ADRD patients with behavioral symptoms.	Acceptability will be evaluated using Likert scale (from 0 [strongly disagree] to 10 [strongly agree]) to answer ten affirmatives regarding the use of home-based tDCS. Safety will be assessed with a questionnaire about side effects that include itching, burning, headache, fatigue, and dizziness.
Secondary Goal	To assess the efficacy of tDCS for ADRD-related symptoms, mainly behavioral symptoms.	Behavioral and cognitive symptoms will be evaluated through validated clinical instruments.

Background Information

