Given the clinical relevance of NPS in ADRD, the equivocal results of the therapeutic resources available to address it, and the emerging evidence of safety and efficacy of tDCS in ADRD, our proposal aims to test the acceptability, safety and efficacy of home-based tDCS for the treatment of NPS in ADRD. Home-based tDCS circumvents critical problems observed in previous trials (16), including the need of multiple visits to medical centers for tDCS application, allowing a more intensive application (e.g. 5 x per week) for long periods.

Objectives

Objectives	Outcome Measures
Primary objective To assess acceptability and safety of providing tDCS to ADRD patients with behavioral symptoms.	Acceptability will be evaluated using Likert scale (from 0 [strongly disagree] to 10 [strongly agree]) to answer ten affirmatives regarding the use of home-based tDCS. Safety will be assessed with a questionnaire about side effects that include itching, burning, headache, fatigue, and dizziness. Acceptability scale will be applied on Week 2, 4, 6 and 12. Side effects questionnaire will be applied on Week 2, 4 and 6.
Secondary objectives To assess the efficacy of tDCS for ADRD on clinical outcomes, mainly behavioral symptoms.	Behavioral symptoms and cognitive measures evaluated through validated tools: NPI, bDAS, CSDD, MMSE. NPI will be applied on Baseline, Week 2, 4, 6 and 12, while bDAS, CSDD and MMSE will be applied on Baseline, Week 6 and Week 12.

Study Design

We will carry out an open-label study to evaluate home-based active tDCS for AD and behavioral symptoms. There will be no randomization. All eligible patients will receive exactly the same treatment. All participants (n=20) will receive active tDCS with a constant current intensity of 2mA. Anodal tDCS will be applied to the left dorsolateral prefrontal cortex, while cathodal electrode will be positioned on the right dorsolateral prefrontal cortex. Caregivers will help setting up and administering tDCS for participants with AD at home. tDCS will be applied for 30min at an intensity of 2mA, with

30 s ramping up and down.

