Recruitment and Retention. Participants will be recruited at the *UTHealth Neurosciences Neurocognitive Disorders Center* ([name]), *UT Physicians Center for Healthy Aging* ([name]), and at the UT Health San Antonio's Glenn Biggs Institute for Alzheimer's and Neurodegenerative diseases Neurology clinic ([name]). Study flyers with summary and contact information about the study will be used at the *UTHealth Neurosciences Neurocognitive Disorders Center* as a mean to provide awareness and information to potential participants. Flyers will be available at the request of potential subjects at the moment of their visit with [name], and at dedicated spaces for research recruitment material in the *UTHealth Neurosciences Neurocognitive Disorders Center*. As serious adverse effects and problems with the device use are not anticipated, it is expected a high retention rate. The remote supervision of the tDCS or sham daily sessions by trained research staff will contribute to the retention of subjects during the trial.

Training plan. Patients will be instructed on treatment at baseline, when they will

receive the device. A trained research staff will instruct the participant's caregiver on how to handle the equipment. All sessions will be remotely supervised by trained research (RA) staff, who will be able to answer questions during the sessions and verify that the device is being used correctly.

Study Procedures

Primary Outcome

Acceptability will be evaluated using the method proposed by Ahn et al. (2019) (21). Participants and/or their caretakers will be asked to apply a Likert scale (from 0 [strongly disagree] to 10 [strongly agree]) to answer ten affirmatives regarding the use of home-based tDCS. For example, question 1: It was easy to prepare the device and accessories, question 7: I felt confident using the device. Overall acceptability across groups will be evaluated by descriptive measures of satisfaction ratings. We expect that participant satisfaction ratings at the end of treatment will demonstrate high acceptance of tDCS treatment in the present sample. Acceptability scale will be applied on Week 2, 4, 6 and 12.

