Safety will be assessed with a questionnaire about side effects that include itching, burning, headache, fatigue, and dizziness (21). The most common side effects of tDCS reported in the literature are very mild and include tingling, burning sensation, and skin redness, while other less common side effects may include headache, sleepiness, dizziness, and difficulty concentrating (22-23). Although rare, a possible adverse event of tDCS is the occurrence of skin lesions or small skin burns on the site where electrodes touch the skin (24-25). The side effects questionnaire will be applied on Week 2, 4 and 6 to assess the incidence and frequency of side effects in our recruited sample. We expect that the occurrence of side effects will be similar to the frequencies reported in the scientific literature, demonstrating that home-based tDCS is a safe and feasible intervention to be used on the management of ADRD patients with behavioral symptoms.

Secondary Outcome

The main efficacy measure will be change on the Neuropsychiatric Inventory (NPI) score (26), the best-validated tool for measuring NPS in dementia patients. This 12-item informant-based interview is a widely accepted measure of NPS in dementia. The NPI consists of a detailed evaluation of the following 12 neuropsychiatric domains: hallucinations, delusions, agitation/aggression, depression, anxiety, irritability, disinhibition, euphoria, apathy, aberrant motor behavior, change in night-time sleep behavior, and changes in appetite and eating (27). Each NPS domain is rated according to its severity (0-3) and frequency (0-4) (28). NPS will be assessed at baseline, during treatment (weeks 2, 4 and 6) and 6 weeks post-treatment. Our hypothesis is that patients receiving tDCS will demonstrate lower NPI scores at the end of treatment.

Other clinical outcome measures will include: (1) total score on the Brief Dimensional Apathy Scale (bDAS) (29); (2) depressive symptoms as assessed by the

Cornell Scale for Depression in Dementia (CSDD) (30); (3) cognition as evaluated by the Mini-Mental State Examination (MMSE), which includes memory, language, praxis and orientation tasks, yielding a global cognition score ranging 0 to 30, with higher scores indicating better performance (31). Our hypothesis is that all participants receiving treatment will demonstrate lower scores on the bDAS and CSDD, and higher scores on the MMSE at the end of treatment.

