The sample of this study consists of 20 older adults aged 60 years-old and over with ADRD and behavioral symptoms. Study participants or their legally authorized representatives will give informed consent. Moreover, caregivers and/or relatives will be required to be present during the clinical assessments and tDCS sessions to ensure reliable information and proper use of the device. Participants will be recruited without any specific regard to sex, race, religion or ethnicity. Patients will be recruited at the UTHealth Neurosciences Neurocognitive Disorders Center, and UTHealth Center for Healthy Aging. We will recruit ADRD patients whose dementia is of mild to moderate severity. Adults younger than 60, adolescents and children are excluded as we are focusing on dementia, an age-related disorder that usually affects individuals aged 60 and older. No other special classes of vulnerable individuals will be included. It is anticipated that the subject demographic profile will mirror the larger population of individuals with ADRD from which they are recruited.

Informed Consent and Assent. Potential subjects and their caregivers/relatives will be informed about the study purpose, procedures, risks and benefits. They will be informed that participation in the research study is voluntary and that they are free to decline to be in the study, or to withdraw from it at any point. Study records will be kept confidential. Study information will be coded, and only study personnel will have access to the files.

Protection Against Potential Risks. The risks to the subjects involved in this study are minimal. To ensure this, we will take necessary steps to reduce risk for all study participants. We will try to create an atmosphere of security and trust prior any clinical assessment in order to minimize any discomfort with the research questions. In addition, subjects are always given permission to not answer questions with which they feel uncomfortable. A number of procedures (e.g. use of identifying numbers instead of names) will be implemented to protect subjects against loss of confidentiality. Side effects related to active tDCS application are uncommon, and mild when present, including: itching and burning sensation on the scalp, mild headache, dizziness, and fatigue. Although rare, a possible adverse event of tDCS is the occurrence of skin lesions or small skin burns on the site where electrodes touch the skin (24-25).

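### The companion is required at all clinical assessments with no exemption for the MMSE, so visit-specific prompting or rehearsal could pass for the hypothesised MMSE rise in this single-arm study

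*Combined protocol and SAP*

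**What the plan says.** The presence rule is in Ethics/Protection of Patient Confidentiality: "caregivers and/or relatives will be required to be present during the clinical assessments and tDCS sessions to ensure reliable information". The sentence adds correct device use as a second reason. It names no visit or instrument to which it does not apply.

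The caregiver also has a part in treatment. The Study Design row of General Information says "Caregivers will set up and administer tDCS for participants with AD at home"; the Study Design section puts it more softly: "Caregivers will help setting up and administering tDCS for participants with AD at home". There is one open-label arm: "There will be no randomization. All eligible patients will receive exactly the same treatment".

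Under Secondary Outcome, the MMSE is one of the other clinical measures: "cognition as evaluated by the Mini-Mental State Examination (MMSE), which includes memory, language, praxis and orientation tasks". The stated hypothesis is a higher score at the end of treatment. Table 1 schedules it at Baseline, Week 6 and Week 12. The same section makes the NPI the leading efficacy measure ("The main efficacy measure will be change on the Neuropsychiatric Inventory (NPI) score") and describes its source: "This 12-item informant-based interview is a widely accepted measure of NPS in dementia".

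The documents do not bar prompting, provide for testing the patient apart from the companion, call for alternate MMSE forms or require an assessor independent of treatment.

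**The concern.** The stated reason for presence, reliable information, fits an informant interview such as the NPI. It fits the MMSE poorly, because the MMSE scores the patient's own performance on memory, language, praxis and orientation tasks. A companion in the room sees the items at Baseline. That person can then rehearse them with the patient before Week 6, or help more at a later visit than at the first. A companion who also helps give tDCS knows the treatment and may hope that it works.

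Any gain from coaching between Baseline and Week 6 enters the MMSE change score in the hypothesised direction. With no concurrent control, the analysis cannot separate it from an effect of tDCS. The plan's minimum evidence threshold is a posterior probability of 0.75, so even a small systematic shift changes how often that threshold is met.

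**Working it through.** **1. Which mechanisms survive in a change score.** Let b0 be the effect of the companion on the Baseline MMSE and b6 the effect at Week 6. The bias in the mean change is b6 - b0.
- Constant help at each visit: b6 = b0, bias 0.
- Rehearsal after Baseline, or help that grows: b6 > b0, bias towards improvement.
- Help at Baseline only: b6 < b0, bias against improvement.

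The presence rule covers all three MMSE visits, so presence alone gives the first case. Only the second produces a false rise.

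**2. The plan's own figure.** The Sample size section states 80% power at N = 20, alpha 0.05 (two-tailed) and d = 0.66, for change from baseline to end of treatment. A paired t test with 19 degrees of freedom and noncentrality 0.66 x sqrt(20) = 2.95 gives 79.9%. The figure reproduces, and this point does not alter it.

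**3. Effect of an assumed shift with no true change.** The documents give no size for the bias, so it is an assumption, in SD units of the change score. With n = 20 the standard error is 1/sqrt(20) = 0.224 SD. Under a near-flat prior, the posterior probability of improvement reaches 0.75 when the t statistic exceeds its upper quartile (about 0.67 on the normal scale). The normal approximation is P(Z > 0.674 - shift/0.224). The table uses the noncentral t with 19 degrees of freedom.

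| Assumed shift (SD of change) | P(posterior probability >= 0.75 for improvement) | P(favourable two-sided p < 0.05) |
|---|---|---|
| 0 | 25% | 2.5% |
| 0.1 | 41% | 6.2% |
| 0.2 | 59% | 13.3% |

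The first row is also the case where the companion's influence is the same at both visits.

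**4. What the shift means in MMSE points.** Assume an SD of six-week change of 2.5 points (range 2 to 3; not in the documents). The standard error is 2.5/sqrt(20) = 0.56. If coaching adds a net 1 to 2 points in a quarter of patients, the mean shifts by 0.25 x 1 = 0.25 to 0.25 x 2 = 0.5 points. Divided by 2.5, that is 0.1 to 0.2 SD, the rows above. By the normal approximation, the same 0.25 to 0.5 points gives 45-67% at SD 2 and 38-53% at SD 3 for the 0.75 threshold. For scale, d = 0.66 corresponds to 0.66 x 2.5 = 1.65 points.

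**5. The near-flat prior.** The default prior for regression coefficients has variance 100. Against a squared standard error of 2.5^2/20 = 0.31, the data carry 100/(100 + 0.31) = 99.7% of the weight, so treating the prior as flat is adequate under that assumption.

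**The case against.** The strongest reply is that the rule sits in an ethics section and does not describe how the MMSE is given. It does not say that the companion is within earshot or may help. The rule allows relatives as well as caregivers, so the companion need not be the person who handles the device. It applies at Baseline too, so presence cancels unless its influence changes between visits, and nothing in the documents shows that it does. Patients see the test at Baseline themselves, so separation would not remove their own practice effect. The MMSE ranks behind the NPI in a 20-person study whose primary goals are acceptability and safety, and a single-arm change is open to other drifts in any case. Separating patients with dementia and behavioral symptoms may also work against the sense of security that the same section wants.

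Most of this limits the point; it does not remove it. The sentence as written covers the MMSE, no safeguard appears elsewhere, and rehearsal of items seen at Baseline is by its nature visit-specific. The worry about separating patients is fair, and the change should allow for it.

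Three stronger readings are tempting and are not supported:
- **That having the companion present raises Week 6 scores in itself.** The same rule at Baseline rules this out unless the influence differs between visits.
- **That the patient's own ratings are biased because the caregiver hears them.** No efficacy scale is identified as a patient self-rating: the NPI is informant-based, and the respondent for bDAS and CSDD is not stated. A rise on those three scales would mean worsening. On acceptability, the plan says "Participants and/or their caretakers will be asked to apply a Likert scale", so the caregiver may be a proper respondent. That scale has no baseline and is summarised descriptively. The documents offer no support for a courtesy effect on acceptability or side-effect answers, and staff also watch for adverse events by live video throughout each session.
- **That 41-59% is the plan's false-positive rate for the MMSE.** It follows only if the assumed shift is real. The 25% starting value comes from the 0.75 threshold, not from the presence rule, and the plan itself grades 75% to 90% as only moderate evidence.

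**Conclusion.** The point holds in a limited form. The presence rule exempts no instrument, the MMSE is a repeated performance test in one unblinded arm, and no text bars coaching or provides for separate testing. Coaching that differs between Baseline and Week 6 would therefore be counted as a tDCS effect on cognition. This is an opportunity for bias, not evidence of it, and its size is unknown. The illustrative increases (to 41-59% for the 0.75 threshold and to 6-13% for a favourable two-sided p < 0.05) rest wholly on an assumed shift of 0.1 to 0.2 SD, no true effect, n = 20 and a near-flat prior.

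The consequence is confined to the MMSE, a secondary outcome. The documents do not support extending it to the acceptability or side-effect outcomes. Requiring a companion is not itself an error, since the informant interview needs one. The change is worth making because it is cheap and protects the only cognitive measure.

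**What to change.** Amend the sentence in Ethics/Protection of Patient Confidentiality, and the visit instructions, along these lines: the caregiver attends each visit and serves as informant, but the MMSE is given with the companion out of the room, or out of view and earshot if it is done by video. Where a patient cannot be separated, the companion must not prompt or help, and the companion's presence is recorded. The MMSE analysis is then repeated without those patients as a sensitivity check only; the main analysis keeps everyone, because 20 patients leave little room for exclusions.

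Keep the setting the same at Baseline, Week 6 and Week 12 for a given patient where possible, since a change of setting between visits would itself fail to cancel. The arrangements for acceptability and side-effect answers can stay as they are.

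The cost is one amended sentence and a few minutes per visit. The downside is that some patients may need the companion nearby, which the exception covers. Separation will not remove the patient's own practice effect or make up for the missing control arm.
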